### **Procedures following partial hospitalization (post-discharge from BHP)**

At discharge as part of treatment as usual participants will create a safety aftercare plan with their BHP provider, and this plan will be gone over in their discharge session with research staff. In addition, staff will provide participants with a list of local crisis resources across the state, and ask participants to identify a few they could contact if needed. In this session we will reiterate that the research team will not be checking patients Weekly Check-Ins (PHQ/GAD) or the EMA surveys. Following discharge from the hospital, patients are expected to follow their aftercare plan with outpatient providers. During this time study staff will not be monitoring safety of any Mood Check ins completed by participants, nor will they be following the daily EMA surveys.

The smart phone app will clearly remind patients as they complete these forms each day that study staff will not see the data and thus, if they feel that they need attention, they should call their outpatient

providers, call 911, use the crisis text hotline, or go to their local Emergency Department. Additionally, if a patient indicates any level of suicidal ideation on the PHQ-9 (item 9 score  $\geq 1$ ), the app will generate a message urging the patient to call their outpatient providers, contact emergency services, or utilize the crisis text line if they are feeling unsafe. Additionally, the list of crisis resources provided to patients upon discharge will be available to view in the app FAQs.

Additionally, any symptom monitoring surveys completed in the Long Term phase will not be monitored at all by staff.

### ***Suicidality***

As part of this study, participants will complete the Columbia Suicide Severity Rating Scale at 1 and 3-month follow-up assessments. Answers of "Yes" to questions 4 or 5 on C-SSRS will result in emergent evaluation by licensed clinician member of study staff ([name]) for appropriate assessment and triage (see risk assessment section below). In addition to clinical interview, as well as when clinical interview cannot be scheduled, participants will complete a self-report version of the C-SSRS. When this occurs, study staff will monitor their responses in real-time, and will ensure that a licensed clinician is available remotely at time of study assessment for emergent evaluation if necessary (Answers of "Yes" to questions 4 or 5). If [name] is unavailable to conduct a risk assessment another pre-determined licensed clinical psychologist will reach evaluate the patient. If multiple risk assessments are required for the same participant, we will attempt to have the same clinician speak with the patient at all risk assessment timepoints

### **Risk Assessment**

Risk assessments for suicidality (*CSSRS*) will be conducted by the close of business on the same day the notification was received. If the study participant has experienced significant deterioration but is not in immediate danger of hurting him or herself, we may take the following actions. First, we will inform the patient about procedures for contacting emergency services should they find themselves at risk for self-harm. Second, we will urge the patient to make an appointment with their outpatient provider as well. Third, with the patient's consent, we will speak with one of their family members so that he/she can be aware of the seriousness of the patient's symptoms and the agreed-upon treatment plan. Fourth, if the patient wishes additional treatment referrals or other referrals, we will facilitate these referrals. [name] will conduct a suicide risk assessment to determine whether it is necessary to take immediate action to prevent the participant from causing harm to themselves. If [name] is unavailable to conduct a risk assessment another pre-determined licensed clinical psychologist will reach evaluate the patient. If multiple risk assessments are required for the same participant, we will attempt to have the same clinician speak with the patient at all risk assessment timepoints. If needed, actions that [name] may take include having a family member bring the person to McLean Hospital or sending an ambulance so that the individual may be evaluated for inpatient psychiatric admission.

### **Documentation**

Study staff will document each time a participant is identified for clinical deterioration or suicidality. Documentation will include the following:

- Date of identification
- Reason for identification (e.g., increase on GAD-7)
- Date and time clinician contacted
- Outcome

## VI. BIOSTATISTICAL ANALYSES

### Phase 1: Development

Not applicable

### Phase 2: Open Trial

The primary aims of this treatment development project are to develop: a) HabitWorks, b) procedures for hospital augmentation and bridge to outpatient care, and c) procedures for a subsequent RCT. First, we will analyze qualitative data obtained from post-treatment interviews and exit questionnaire. The PI will content analyze audio recordings using a rapid coding technique. Audio recordings will then be transcribed verbatim and analyzed with more conventional analytic methods. Using the constant comparison method from grounded theory transcripts will be read for emerging themes. After independently categorizing thematic clusters, the scientific team will create a coding scheme to organize data, prepare a written report detailing the emerging themes, and discuss results with the advisory board.

We will compare outcomes to a **priori target outcomes** (see Table) after each iteration of the open trial. We will calculate descriptive statistics (e.g., mean, frequencies) to evaluate whether the target outcome was met. When the target is not met, this will prompt a discussion with the team and advisory board about potential modifications. We will calculate effect size estimates to characterize pre-post differences (open trial) and the associated 95% CIs, to understand the precision, or lack thereof, of our estimates.

Target Outcomes	
Target Engagement:	75% of HabitWorks group moves into normal range  of interpretation bias (Benign endorsement = 70%; Negative endorsement = 30%) on the WSAP and on the Scenario Recognition Task ( Similarity rating (1 to 4) for target sentences: benign = 2.3; negative = 1.9).
Treatment Credibility & Expectancy:	Average = 5 (moderate credibility or 50% expectancy)
Retention:	75% of participants complete the 3 month-assessment 75% of participants complete HabitWorks daily during acute treatment 50% of participants complete HabitWorks 3x week in transition phase
Satisfaction:	Average rating 5 or above (on a 1 to 7 scale) on the Exit Questionnaire
Treatment response:	50% of HabitWorks group responds to treatment (“much or very much improved” on CGIS) and 20% reduction in functional impairment in HabitWorks group with a clinically meaningful between group effect size of $d = .40$

**Case series:** We will report results from 4 participants from the Phase 2 open trial and the Phase 3 randomized controlled trial in a case series format. We will report data on app usage, clinical outcomes, and app feedback collected throughout the project. In all 4 participant case reports, we will remove any identifiable information, and will report limited demographic information (e.g., age range, gender, race, and ethnicity).

**EMA data.** We will pilot the use of EMA methods and anticipate following a similar analytic strategy as prior EMA work. In brief, we will examine change in affect using repeated measures ANOVA. We hypothesize that individuals who complete the WSAP just prior to the random EMA PANAS-X assessment will report an increase positive affect and a decrease in negative affect from the prior EMA assessment. We will primarily rely on Latent Growth Models (LGM) due to our interest, and hypotheses, related to HabitWorks administration and change in interpretation events. LGM provides a flexible, powerful, and easily interpreted statistical approach to examine affective and cognitive change modeled around a discrete event. We first construct models for negative and positive affect; these models will initially be specified as parallel growth processes to account for shared variance, but will be tested individually if a parallel growth model cannot be fit. We will estimate intercept (i.e. mean) and slope (i.e. linear

rate of change over time) for each of these constructs using the anchor event (i.e. HabitWorks session) and 1-2 EMA assessments before and after, providing 3-5 time points to model change. Should linear slope poorly describe the data, we will investigate nonlinear slope or specify piecewise, discontinuous, linear growth processes. We first fit unconditional models to determine the optimal change trajectory for each outcome. Once an optimal growth trajectory has been identified, we regress growth parameters (i.e. intercept and slope) on changes in WSAP responses to examine the association of intercept and slope of interpretation bias outcome variables with affect and symptoms.

**Power analysis.** One goal of the current project is to determine the recruitment rate at our site, and to compare it to the rate needed for an adequately powered RCT (i.e., 4 individuals per month = 200 participants over 50 months (estimated recruitment duration of a subsequently proposed RCT)). Our primary hypothesis for the subsequent RCT is that HabitWorks will be superior to control on our primary outcomes. We determined that a clinically significant difference for a low-intensity, augmentation treatment is an effect size of  $d = .40$ , which corresponds to a post-treatment between-group difference of 2.8 points on the WSAS. We conducted preliminary power analyses using these numbers and a 15% dropout rate (based on our pilot studies). We estimated that a sample size of 200 would give us >80% power to detect a group difference of  $d = .40$ . This effect appears feasible, given that our pilot RCT resulted in a between-group effect size of  $d = .63$  on a measure of well-being.

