**Ecological Momentary Assessment (EMA)**

We will pilot the use of EMA to assess fluctuations in positive and negative affect using the PhenX Toolkit recommended measure PANAS-X. During the 1-month transition phase, participants will complete the PANAS-X 4 times every day via the smartphone app. The surveys will be administered at random times during each one of 4 stratified blocks of time (9am-12pm, 12-3pm, 3-6pm, 6-9pm).

Other interview measures will include:

The Longitudinal Interval Follow-Up Evaluation (LIFE) to assess psycho-pharmacotherapy use, including any medication or dosage changes.

Study staff will conduct a qualitative exit interview with prompts about overall patient experiences, acceptability and feasibility, relevance of the stimuli, and user-experience of the app.

Treatment adherence. Number of sessions completed will be recorded by the app and will be used as both a measure of feasibility/ acceptability, and as needed as a control variable in analyses.

**Compensation**. Participants will receive compensation for their time to complete assessments. Participants will receive \$20 for the eligibility assessment and pretreatment assessment, and an additional \$20 for the post-treatment assessments. They will receive \$30 for the 1-month and 3-month follow-up assessments, \$30 for completing at least 80% of the EMA surveys each week for 1 month, and \$20 for the post-treatment qualitative interview (open trial only).

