**Compensation.** Participants will receive compensation for their time to complete assessments. Participants will receive \$20 for the pretreatment assessment, and an additional \$20 for the post-treatment assessments. They will receive \$30 for the 1-month and 3-month follow-up assessments, and \$20 for the post-treatment qualitative interview (first 20 participants only). Participants will also be compensated for completing EMA surveys- they will receive \$10 each week they complete any surveys at all, and a bonus \$30 for every week they complete 70% surveys (19/28).

If, for whatever reason, a participant cannot or will not accept checks, the study will compensate with a one-time \$50 giftcard.

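### Repeated measures ANOVA is named for change in EMA affect although sessions and answered prompts will differ between participants, and no rule for missed prompts is given

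*SAP*

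**What the plan says.** The EMA paragraph of the SAP (VI. Biostatistical Analyses, Phase 2: Open Trial) says "we will examine change in affect using repeated measures ANOVA". The hypothesis beside it is a before/after contrast. Participants who have just done the WSAP should show a rise in positive affect and "a decrease in negative affect from the prior EMA assessment". The same paragraph continues: "We will primarily rely on Latent Growth Models (LGM"), fitted around each HabitWorks session with "1-2 EMA assessments before and after, providing 3-5 time points to model change". SAP Phase 3 states that similar EMA analyses will be done in the RCT.

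The Protocol's EMA section says that "participants will complete the PANAS-X 4 times every day via the smartphone app" during the transition month, at random times within four daily blocks. The open trial pays "for completing at least 80% of the EMA surveys each week for 1 month". The RCT makes a base payment for "each week they complete any surveys at all" and adds a bonus "for every week they complete 70% surveys (19/28").

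Neither document says what happens to a missed prompt, in the ANOVA or in the growth model. The growth-model estimator is not stated either.

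**The concern.** Standard repeated measures ANOVA needs the same complete set of occasions from every participant. These data will not have that form. RCT participants are asked for at least three sessions a week, and the SAP's own retention target is that only half of participants reach three a week in the transition phase. The number of session windows will therefore vary even if every prompt is answered. The payment rules also foresee missed prompts. When one prompt of a pair is missing, a complete-case ANOVA drops the pair and with it the answered prompt.

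Two things are at stake. Precision is lost, although the SAP stresses the precision of its estimates. In addition, if non-response is related to mood, the retained pairs may misstate the change in affect after a session.

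**Working it through.** **The plan's own figure.** 4 prompts × 7 days = 28 a week. 0.70 × 28 = 19.6, which rounds down to the stated 19. As a share, 19/28 = 67.9%, so both 70% and 67.9% are used below.

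**Incomplete pairs.** With response probability p and independent responses, the incomplete share is 1 − p². With correlation ρ between adjacent responses it is 1 − [p² + ρp(1 − p)]. The documents give no ρ; 0 and 0.3 are shown as assumptions.

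| Payment level | p | Incomplete, ρ = 0 | Incomplete, ρ = 0.3 | Four-prompt window complete (p⁴) |
|---|---|---|---|---|
| Open trial | 0.80 | 36% | 31% | 41% |
| RCT bonus, 70% | 0.70 | 51% | 45% | 24% |
| RCT bonus, 19/28 | 0.679 | 54% | 47% | 21% |

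The share falls below half once p exceeds √0.5 = 0.707. At p = 0.70 it does so once ρ exceeds 0.05, and at 19/28 once ρ exceeds 0.18.

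**People retained.** Three sessions a week for four weeks is about 12 windows. Expected complete pairs per person are 12 × 0.49 = 5.9 at 70% and 12 × 0.64 = 7.7 at 80%. The chance of having none at 70% is 0.51¹² ≈ 0.0003.

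**Precision.** This was simulated with 32 participants (half of the initial RCT target of 64) and 10 to 12 sessions each, at 70% response unrelated to mood, with assumed variances. Both methods are unbiased. In one setting the standard error is 0.047 for a mixed model with participant and window effects, and 0.058 for person-mean complete-pair differences. 1 − 0.047/0.058 = 19% smaller. Across settings the mixed-model standard error is about 15% to 20% smaller. Put the other way, the complete-pair standard error is about 18% to 25% larger (1/0.85 = 1.18; 1/0.80 = 1.25).

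**Bias.** This was simulated with 100,000 pairs and a true change of 0.20 SD, higher scores meaning better mood. Assumptions not in the documents: before/after correlation 0.3 to 0.7, and odds ratio of response 1.5 to 2.0 per SD of mood. The table is for 70% response. In the first and third rows the before-prompt is always answered.

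| Why a prompt is missed | Complete pairs | Likelihood, all answered prompts |
|---|---|---|
| After-prompt missed because of low mood at the answered before-prompt | 0.08 to 0.16 | 0.20 to 0.21 |
| Each prompt missed according to its own mood, same rule | 0.19 to 0.20 | 0.19 to 0.20 |
| After-prompt only, according to its own unseen mood | 0.23 to 0.33 | 0.26 to 0.36 |

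In the first row at 80% response, complete pairs give 0.12 to 0.18. With no true change, the first mechanism at 70% gives complete-pair estimates of −0.03 to −0.14. The retained pairs start from better mood than average and regress towards the mean, so improvement is understated.

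**The case against.** The strongest reply is that growth models, not ANOVA, are the main EMA analysis. They can use partial windows, and the ANOVA is mentioned only in brief, with reference to earlier EMA work whose handling of missed prompts cannot be seen here. EMA is a pilot measure. It is not listed under Aim 2 and has no row in the target-outcomes table, so no go/no-go decision depends on this ANOVA. All of that stands and limits the weight of the point. It does not remove the named method. Growth models keep partial windows only if fitted by full-information maximum likelihood, which the SAP does not say.

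A reader might infer three stronger things that the documents do not support.

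- **That most pairs will be incomplete.** This holds only at the RCT bonus level, narrowly, and with nearly independent responses. It fails at the open trial's 80%. A bonus threshold is not a forecast, and the RCT also pays for any response in a week, so actual completeness is unknown.
- **That almost nobody would be analysable.** The chance that one person has all 12 pairs complete is 0.49¹² ≈ 0.02% at 70%, but the SAP does not specify a 12-occasion complete-case ANOVA. With person means, almost everyone stays in.
- **That non-response linked to mood always biases the ANOVA and that a mixed model cures it.** The second and third rows of the bias table show otherwise. In the third, the likelihood estimate is slightly further from the truth than complete pairs.

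**Conclusion.** The point holds in a limited form. The SAP names a method that does not suit unbalanced EMA data and gives no rule for missed prompts. Roughly one third to one half of before/after pairs would be incomplete at the paid thresholds if responses were independent, and fewer if adjacent responses are correlated. The loss of precision rests on assumed variances and 70% response, and is smaller when response is higher. The bias is conditional: it is material if low mood at an answered prompt leads to a missed next prompt, and close to zero if both prompts are missed by the same own-mood rule. No likelihood method repairs missingness that depends only on the unseen after-prompt mood. The change is worth making, but it does not affect the trial's main conclusions.

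**What to change.** In the SAP's EMA paragraph, and through Phase 3 for the RCT:

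1. Replace the repeated measures ANOVA with a linear mixed model (REML) on every answered prompt, with random effects for participant and session window. Report the change with its 95% CI.
2. State that the latent growth models are fitted by full-information maximum likelihood, so that partly observed windows are kept.
3. State the missing-at-random assumption, and add a simple sensitivity analysis for mood-dependent non-response, for example by shifting the affect assumed at missed after-prompts over a stated range.

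The cost is a few sentences and a little more analysis in standard software. No new data are needed.

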**HabitWorks**

Participants assigned to HabitWorks will complete the same procedures as outlined in the Open Trial. Specifically, participants will complete a task designed to improve interpretation biases. During each session, participants complete the previously validated word-sentence association paradigm (~10 min). The task presents ambiguous sentences (“You failed an exam”) and provides positive feedback (“you are correct!”) when participants endorse benign interpretations/attributions (“difficult test”) and negative feedback (“you are incorrect!”) for negative interpretations/attributions (“stupid”). Sessions during the transition phase are shorter (~5 min).

Once enrolled, participants will be asked to complete HabitWorks daily on their smart phones in a quiet room while attending the partial hospital, at least three times per week at home for 1-month following discharge, and as desired during the final 2 months. During the 1-month post-acute period, participants may complete assessments of symptoms (PHQ-9 and GAD-7) as often as desired, including optional once weekly check-ins for the study. For people in the HabitWorks condition, these surveys are administered via the HabitWorks app.

During the 1-month post-discharge period, participants will also complete daily assessment of affect (see EMA description in Measures). These surveys will be administered via Metricwire. The HabitWorks and Metricwire app was designed to protect participants' privacy, confidentiality, and data security. Only research personnel will have access to study information. Data collected by the Metricwire app is encrypted, and downloaded by the researcher to the local research server in a de-identified format (i.e., subject ID number). The local research server is only accessible by study staff. Study staff will provide orientation to the app and answer any questions regarding the assessments and data collected.

HabitWorks Treatment phase	Location	Frequency of sessions	Duration
---------------------------------------	-----------------	------------------------------	-----------------

Acute (1 to 14 days)	Hospital	Daily to augment CBT-based hospital treatment	10 min
Transition (1-month)	Home	3x per week to transition from intensive hospital to outpatient care, 4x daily affect surveys, weekly symptom monitoring survey	15 min/day

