### **Phase 3: Randomized Controlled Trial**

We will conduct similar qualitative, descriptive, and EMA analyses as noted in the open trial. We will calculate effect size estimates to characterize between group differences and the associated 95% CIs, to understand the precision, or lack thereof, of our estimates.

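### The RCT reuses the open trial's session-anchored EMA analysis, whose before/after test has no time-of-day term or no-session comparison, so ordinary daily change in affect can mimic or hide a session effect.

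*SAP*

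**What the plan says.** The SAP's Phase 3 section gives one instruction for EMA in the RCT: "We will conduct similar qualitative, descriptive, and EMA analyses as noted in the open trial". It adds, for outcomes in general, "We will calculate effect size estimates to characterize between group differences and the associated 95% CIs".

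The analyses carried over are in the EMA paragraph of the SAP's Phase 2 section:

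- A repeated measures ANOVA of change in affect. The hypothesis is that people who did the task shortly before a survey "will report an increase positive affect and a decrease in negative affect from the prior EMA assessment".
- Growth models, named as the main approach, built "using the anchor event (i.e. HabitWorks session) and 1-2 EMA assessments before and after, providing 3-5 time points to model change". A nonlinear or piecewise shape is the fallback if a straight line fits poorly.
- A final step: "Once an optimal growth trajectory has been identified, we regress growth parameters (i.e. intercept and slope) on changes in WSAP responses".

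On timing, the Protocol's EMA section says that during the transition month "participants will complete the PANAS-X 4 times every day via the smartphone app", and "The surveys will be administered at random times during each one of 4 stratified blocks of time", running from 9am to 9pm. HabitWorks sessions are to be done "at least three times per week at home for 1-month following discharge", with no time of day given. The Protocol's Phase 1 text says that the app prompts sessions at set times but names none. The Symptom Tracking arm completes the same EMA and has no HabitWorks session.

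**The concern.** A change from the rating before a session to the rating after it has two parts: whatever the session did, and whatever affect would have done over that stretch of the day anyway. Separating them needs a comparison interval at the same time of day without a session, or at least a time-of-day term. The SAP names neither for the before/after test. Ordinary daily movement could therefore be reported as a session effect, or could cancel a real one.

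The approach was written for a single-arm study. In the RCT, control participants supply the same ratings, but an analysis anchored on a session gives them no place unless matched windows are defined for them. The session-level result could feed into the planned larger trial, so misattribution would matter even in a pilot.

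**Working it through.** **The SAP's own figure.** One rating each side plus the session gives 1 + 1 + 1 = 3 points; two each side gives 2 + 1 + 2 = 5. The stated 3 to 5 is reproduced. No affect rating at the session itself is described, so the surveys supply 2 to 4 affect values per window.

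**Inputs from the documents.** Four ordered survey blocks per day (Protocol, EMA). About 3 × 4 = 12 home sessions in four weeks (Protocol, HabitWorks). RCT size 64 (Subject Selection) or 84 (Study Procedures).

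**Assumptions.** Allocation 1:1, so 32 or 42 per arm; within-person SD of 1; correlation .4 between adjacent ratings; linear drift of *b* SD per block, resetting overnight; two-sided 5% test; no true session effect. Let *p* be the share of sessions between one day's last survey and the next day's first.

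**Expected shift.** A daytime window moves by +*b*. An overnight window moves by −3*b*, because affect returns from the fourth block to the first. The mean shift is

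*b*(1 − *p*) − 3*bp* = *b*(1 − 4*p*).

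It is zero at *p* = 25%.

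**Rejection rate.** The standard error of the mean before/after change is √[2(1 − .4)/(12*n*)]: .049 at *n* = 42 and .056 at *n* = 32. At *b* = .1, *p* = 0 and *n* = 42, the ratio is .10/.049 = 2.05. The table sets the noncentral-*t* rate beside a simulation of 1,500 trials per cell.

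| *b* | *p* | *n* per arm | Shift (SD) | Calculated | Simulated |
|---|---|---|---|---|---|
| .10 | 0 | 42 | +.10 | 52% | 53% |
| .10 | 15% | 42 | +.04 | 13% | 13% |
| .10 | 25% | 42 | 0 | 5% | 5% |
| .05 | 0 | 42 | +.05 | 17% | 16% |
| .05 | 15% | 42 | +.02 | 7% | 7% |
| .10 | 0 | 32 | +.10 | 41% | 42% |

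With 70% of ratings completed (*b* = .1, *p* = 0, 42 per arm), the simulated rate is 26%.

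**A different drift shape.** A separate simulation used curved drift (block values 0, 1.5, 2 and 1.5 units) with sessions in the first two daytime gaps, 400 runs per cell. At .05, .10 and .20 SD per unit, the before/after test rejected in 11–12%, 29–34% and 76–81% of null trials. Matched no-session windows in the same person gave 3–7%, and clock-matched control windows 4–7%.

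**Masking.** With a true effect of +.15 SD, drift of −.1 and daytime sessions, the before/after estimate is .15 − .10 = +.05 SD. At 42 per arm it is detected in 17% of trials by calculation (16% simulated). A same-block no-session comparison recovers +.15 SD and detects it in 91%; matched control windows recover +.15 SD and detect it in 57%.

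**Piecewise fallback.** With one rating each side, a step plus a slope has three parameters and a design of rank 2, so it is not identified. With two each side and pure linear drift of 1 unit per block, the fitted step is 0 for a session at 15:00 but about +2.1 units at 12:00 or 18:00, because one rating then falls on another day.

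**Regression on WSAP change.** With WSAP change simulated as unrelated to drift, this rejects in 4–7% of null trials.

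**The case against.** Much of the case on the other side stands.

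- *The main EMA inference is elsewhere.* The SAP relies chiefly on growth models and regresses their parameters on WSAP change, which drift common to everyone barely touches. The unconditional growth models choose a shape, and no test of their slope is declared. The problem belongs to the before/after hypothesis.
- *The hypothesis concerns sessions completed shortly before a survey.* Many overnight windows may not qualify, so results that rest on a large overnight share should carry little weight. The daytime case is unaffected.
- *Two affect scales are predicted to move.* If both must reject, 53% becomes .53 × .53 = 28% when both drift favourably with independent errors, and .53 × .025 = about 1% when only one drifts. The SAP gives no decision rule.
- *An arm contrast is not absent.* A reader might infer that the RCT has no between-arm EMA analysis. The documents do not support that: the general effect-size statement could apply, and the assessment schedule lists the EMA PANAS at Pre, Post, 1 month and 3 months. What is missing is how the repeated ratings would enter.
- *EMA is a pilot, described in brief with reference to prior work.* That limits the weight of the point, but the before/after hypothesis is stated and directional.

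The same-block comparison also has limits. If sessions follow mood arising between ratings (assumed log-odds of .25 and .5 per SD, no drift), before/after is biased by +.19 and +.38 SD, the no-session comparison by +.23 and +.44, and matched control windows by +.19 and +.38. Under another model of such selection, before/after was unbiased and the no-session comparison was off by +.09 to +.19. It therefore removes drift, not selection on mood.

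**Conclusion.** The point holds for the before/after test as written: without a time-of-day term or a no-session comparison, it cannot be read as a session effect. The illustrative +.10 SD shift and rejection in about half of null trials depend on assumed drift of .1 SD per block, daytime sessions, full completion and 42 per arm on one scale. With weaker drift, mixed timing or missing ratings, inflation is smaller; at 25% overnight sessions it vanishes. The documents give neither drift nor session timing, so size and sign are unknown.

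A reader might infer that the collected data cannot separate the two effects, or that all EMA results are compromised. Neither follows: sessions at about three per week leave session-free days, both arms are rated in the same blocks, and the regression on WSAP change is largely robust to common drift. CGIS and WSAS are untouched. This is a point to consider, worth settling before analysis.

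**What to change.** Amend the SAP's Phase 3 section.

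1. Name as the RCT's EMA analysis a between-arm mixed model of all PANAS-X positive and negative affect ratings. Include arm, day, block of day, baseline affect (the schedule lists the EMA PANAS at Pre) and participant random effects, and report a 95% CI. As a guide to precision, a person-mean analysis adjusted for baseline has a half-width of about 1.99 × √[2 × ICC × (1 − *r*²)/*n*]. With assumed ICC of .3 to .6 and *r* = .5, this is about .21 to .29 SD of a single rating at 42 per arm (.21 to .30 simulated).
2. Keep the session-anchored analysis as secondary and observational. Add block-of-day terms and compare session intervals with same-block no-session intervals, adjusted for prior affect, or with matched windows in the control arm. State that this removes time-of-day drift but not selection on mood between ratings, so it supports no treatment-effect claim.

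The cost is SAP wording and modest programming, since both arms already supply the data. The price is a more cautious reading of the session-level result.
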